10.3 Termination of Study

The decision regarding continuation or termination of the study will be solely based on safety data, and will be made by the DSMB. Interim analyses will be performed by the DSMB upon request by the co-PIs. The co-PIs will meet every month (or sooner in case of unanticipated SAE) to discuss enrollment, withdrawals, and adverse events. If protocol modifications are warranted, close consultation with the DSMB and IRB will be required, and their approval will be needed.

11) STATISTICAL CONSIDERATIONS

11.1 Study Hypothesis

We hypothesize that IL-1 blockade with Anakinra will improve aerobic exercise performance and reduce hospital admission rates in patients with recently decompensated systolic HF. As the first step in testing this hypothesis, we propose a randomized, double-blinded, pilot study to determine the effect of anakinra on aerobic exercise performance over the course of 6 months. Although this pilot study will not be powered to detect differences in the 6-month hospital admission rates, we believe this study will provide an estimate of the potential effect. An improvement in aerobic exercise performance alone would represent a valuable achievement in this HF population, and would provide the rationale—especially if paired with a signal showing reduced readmission rates—for a subsequent Phase III clinical study to evaluate IL-1 blockade on the key outcomes of HF morbidity and mortality.

11.2 Sample Size Considerations

The sample size for this pilot study is calculated according to the primary endpoint of

difference in interval change in peak VO_2 at 24 weeks between anakinra and placebo. Given an expected average peak VO_2 of 15 mL/kg/min for HF patients, 68 subjects randomized to anakinra and 34 subjects randomized to placebo (2:1 randomization) would provide approximately >95% power to detect a difference of 1.6 $\text{mL}\cdot\text{kg}^{-1}\cdot\text{min}^{-1}$ (standard deviation of 1.7-2.0 $\text{mL}\cdot\text{kg}^{-1}\cdot\text{min}^{-1}$) in peak VO_2 on top of placebo. A conservative estimate of 20% loss to follow-up or withdrawal would retain >90% power.

		Effect size of treatment on top of placebo				
	$\text{mL}\cdot\text{kg}^{-1}\cdot\text{min}^{-1}$	+1.2	+1.4	+1.6	+2.4	+3.2
Standard Deviation	2.3	0.70	0.83	0.91	>0.99	>0.99
	2.0	0.82	0.92	0.97†	>0.99	>0.99
	1.7	0.92	0.98	0.99	>0.99	>0.99
	1.4	0.98	0.99	>0.99	>0.99	>0.99*

11.3 Statistical Analysis

11.3.1 Demographics and Baseline Characteristics

Descriptive summaries of continuous measurements will be reported as median and interquartile ranges due to potential deviation from Gaussian distribution. Descriptive summaries of categorical measurements consist of frequencies, proportions and 95% confidence intervals, when applicable. All analyses will be conducted after database locking once all data has been gathered and electronically captured. All analyses will be based on the intention-to-treat principle (i.e., analyzing groups as randomized and including all patients with outcome data available). The difference in interval changes in peak VO_2 at 24 weeks between the anakinra vs. placebo groups will be compared using random-effect analysis of variance for repeated measures to analyze the effects of treatment within each group and the effect of time_x_group allocation. Unadjusted p-values will be reported throughout, with statistical significance for the primary endpoint set at the 2-tailed 0.050 level. To evaluate the group differences in the secondary endpoints, data will be compared across all groups using the random-effect analysis of variance for repeated measures as indicated above for paired analyses, or Kaplan-Meier curves with Log-rank testing for event rates.

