5.1 Primary Endpoint(s)

Placebo-corrected changes in peak VO₂ at CPX after 24 weeks of treatment will be considered the primary endpoint. This will compare patients treated with anakinra (N=68) vs placebo (N=34), and provide a randomized, double-blinded assessment of the effects of IL-1 blockade on aerobic exercise performance. The data will be collected and electronically transferred to the core laboratory at the University of Illinois, Chicago, IL ([name]).

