6.4 Alternate Consent Group

The subjects who are eligible to enroll in the study but decline to participate will be asked to sign an alternate consent that allows the research team to access the electronic health record for 6 months after the enrollment and make one follow up telephone call at the end of the 6 months period if needed to ascertain vital status and incidence of new event. This alternate consent group will provide an estimate of the event rate in a group free of other research interventions.

7) STUDY DESIGN

[figure not shown]
We designed a single center, placebo-controlled, double-blinded randomized study of Anakinra in patients with recently decompensated systolic heart failure. Patients will undergo baseline clinical assessment, CPX, echocardiogram, non-invasive hemodynamics, and blood tests for biomarkers. The CPX, the echocardiogram, non-invasive hemodynamics and blood tests will be repeated at each visit (6, 12 and 24 weeks). See Schematic of Study Design.

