7.1 Clinical Assessment

A physician on the research team will conduct a thorough clinical assessment and review of the chart at time of enrollment to evaluate for all inclusion and exclusion criteria. Some of the information needed to determine eligibility may be missing, in which case additional testing would not be performed prior to consenting, and it would be completed only after the patient provided informed consent and it would be charged to the study charge account.

A clinical evaluation will also be completed at Visit 1.5 (14±3 days) to determine tolerability of the treatment and side effects, medication reconciliation and completion of a complete blood cell count with differential and basic metabolic panel.

Visits 2 (6±1 weeks), 3 (12±1 weeks) and 4 (24±2 weeks) will include a clinical safety evaluation as well as assessment of the endpoints. Additional visits may be scheduled as needed.

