11.3.3 Analysis of the Primary Endpoint

The data will be collected and electronically transferred to the core laboratory at the University of Illinois, Chicago, IL, where [name], PhD, will analyze data at the end of the study. After locking the database, he will be provided a group allocation according to treatment A or B (blinded to real treatment). The data will be analyzed according to blinded group allocation and the description of the group allocation will be disclosed only after completion of the analysis. The differences in interval changes between the treatments will be compared using random-effect analysis of variance for repeated measures to analyze the effects of time and group allocation. Unadjusted p values will be reported throughout, with statistical significance set at the 2-tailed 0.05 level. All analyses will be based on a 'complete case' approach.

DSMB CHARTER**Charter, Data and Safety Monitoring Board for**

NHLBI 1R34HL118348-01A1

Interleukin-1 blockade in heart failure with preserved ejection fraction:

REcently Decompensate Heart failure Anakinra Response Trial -2

(REDHART2)

Updated on October 25, 2018

DSMB Liaison: [name] – [contact]

1 Introduction

This Charter is for the Data and Safety Monitoring Board (DSMB) for the study: **Interleukin-1 blockade in recently decompensated heart failure: the REcently Decompensated Heart failure Anakinra Response Trial-2 (REDHART2)**, hereafter referred to as “REDHART2”.

The Charter is intended to be a living document. The DSMB may wish to review it at regular intervals to determine whether any changes in procedure are needed.

2 Responsibilities of the DSMB

The DSMB is responsible for safeguarding the interests of study participants, assessing the safety and efficacy of study procedures, and for monitoring the overall conduct of **REDHART2**.

The DSMB is an independent group advisory to the investigators, and is required to provide recommendations about starting, continuing, and stopping the study **REDHART2**. In addition, the DSMB is asked to make recommendations, as appropriate, to the investigators about:

- Participant safety
- Benefit/risk ratio of procedures and participant burden
- Selection, recruitment, and retention of participants
- Adherence to protocol requirements
- Completeness, quality, and analysis of measurements
- Amendments to the study protocol and consent forms
- Notification of and referral for abnormal findings

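### The primary repeated-measures model does not state its covariance, week-24 contrast or degrees-of-freedom method; on its usual reading the week-24 standard error is too small if correlation falls with time

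*Combined protocol and SAP*

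**What the plan says.** Section 5.1 defines the endpoint: "Placebo-corrected changes in peak VO₂ at CPX after 24 weeks of treatment will be considered the primary endpoint". Section 5.2 makes changes at 6 and 12 weeks secondary.

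Section 11.3.1 says that the 24-week changes "will be compared using random-effect analysis of variance for repeated measures to analyze the effects of treatment within each group". The same sentence goes on to name an interaction term: "the effect of time_x_group allocation". Section 11.3.3 says that they are "compared using random-effect analysis of variance for repeated measures to analyze the effects of time and group allocation". Both set a two-sided 0.05 level.

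Neither section says which random effects are fitted, what residual covariance applies, which visits enter, or how degrees of freedom are obtained. Neither says whether the primary p-value is the week-24 contrast or the overall interaction.

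On timing, Section 7.1 states: "Visits 2 (6±1 weeks), 3 (12±1 weeks) and 4 (24±2 weeks) will include a clinical safety evaluation". Section 7.4 puts exercise tests at baseline and at each of these visits. Section 11.3.2 carries the last observation forward at both 12 and 24 weeks for the primary analysis.

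On size, Section 11.2 states that "68 subjects randomized to anakinra and 34 subjects randomized to placebo (2:1 randomization) would provide approximately >95% power" for a difference of 1.6 mL/kg/min with an SD of 1.7-2.0.

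**The concern.** The method's name usually means one random patient effect plus one residual variance. That structure gives every pair of visits the same correlation, whether the visits are 6 or 24 weeks apart. The residual is pooled over all gaps and then applied to baseline versus week 24, the longest one.

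If tests close together agree better than tests far apart, the pooled residual is too small for that contrast. The confidence interval is then too narrow and the nominal 0.05 level is exceeded. Because the plan leaves the structure open, it could also be chosen after the data are seen.

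**Working it through.** **1. The plan's own power figure.** Section 11.2 reproduces as a two-group comparison of 24-week changes.

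- SE = 2.0 × sqrt(1/68 + 1/34) = 0.420. Power = Φ(1.6/0.420 − 1.96) = Φ(1.849) = 0.968; the table gives 0.97.
- After 20% loss (54 vs 27), SE = 2.0 × sqrt(1/54 + 1/27) = 0.471. Power = Φ(3.394 − 1.96) = 0.924, which agrees with the stated >90%.
- All 20 table cells reproduce within 2 points.

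The sample size therefore rests on the SD of the 24-week change itself, not on a pooled residual.

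**2. Formula for the standard error.** Take four visits, group-by-visit means and equal variance at each visit. Let r24 be the baseline-to-week-24 correlation and r̄ the mean of the six pairwise correlations.

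- True variance of the contrast: 2σ²(1 − r24)(1/68 + 1/34).
- Random-intercept model: 2σ²(1 − r̄)(1/68 + 1/34).
- Reported SE / true SE = sqrt((1 − r̄)/(1 − r24)).
- Type I error ≈ 2(1 − Φ(c × ratio)), where c = 1.968 is the t critical value on 3 × 100 = 300 degrees of freedom.

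**3. One case in full.** Assume correlations of 0.813, 0.735, 0.664 and 0.600 at gaps of 6, 12, 18 and 24 weeks. Visits at 0, 6, 12 and 24 weeks give two pairs at 6 weeks, two at 12, one at 18 and one at 24.

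- r̄ = (2 × 0.813 + 2 × 0.735 + 0.664 + 0.600)/6 = 0.727.
- Ratio = sqrt(0.273/0.400) = 0.827.
- Type I error = 10.4% with c = 1.968, or 10.5% with c = 1.96. Simulations of 68 vs 34 gave 10.1%-10.9%.
- At SD 2.0 the true 95% half-width is 1.984 × 0.420 = 0.83 mL/kg/min. The model would report 1.968 × 0.827 × 0.420 = 0.68.

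**4. The range.** Every correlation here is an assumption.

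| Assumed pattern | SE ratio | Type I error |
|---|---|---|
| Constant, 0.80 | 1.00 | 4.9% (simulated 5.2%) |
| Decay (0.90 at 6 weeks) plus 30%-80% visit noise | 0.90-0.98 | 7.6%-5.3% |
| Nearly flat, 0.84 to 0.80 | 0.94 | 6.5% (simulated 6.7%) |
| 0.87 to 0.80 | 0.89 | 8.1% (simulated 8.2%) |
| 0.813 to 0.600 | 0.83 | 10.4% |
| Stable patient share 0.7 plus decay | 0.96-0.76 | 5.9%-13.4% |
| Pure exponential, 6-week r from 0.70 to 0.98 | 0.82-0.74 | 10.8%-14.5% |

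A ratio near 0.905, between the nearly flat and the 0.87-to-0.80 cases, gives 7.5%. Moderate decay therefore spans about 7.5%-10.5%.

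**5. Other readings of the text.**

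- Overall 3-degree-of-freedom time-by-group test, same kinds of decay, no carried-forward values: 5.1%-6.9%.
- Baseline and week 24 only: there is a single correlation, the interaction equals the t-test on change, and the ratio is 1.00. Simulated type I error is 4.6%-5.2%.

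**6. Carried-forward values.** With 20% carried forward, simulated type I error of the random-intercept contrast moved from 5.2% to 5.6% (constant correlation), from 5.9% to 6.8% (mild decay) and from 13.1% to 13.6% (exponential, 0.90 at 6 weeks). The t-test on change stayed at 4.8%-5.2%.

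**The case against.** **Equal correlation is not written.** A reader might infer that the plan specifies compound symmetry. It does not: a random slope or another covariance would also fit the words. This stands, and it makes the finding conditional.

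**The model may hold only baseline and week 24.** The endpoint is the 24-week change and the earlier visits are secondary, so this reading is possible and has no inflation. It is the less well supported one. Section 11.3.2 imputes week 12 as well as week 24 for the primary analysis, and a two-visit model would not need week 12. The remark about paired analyses in 11.3.1 is in the sentence on secondary endpoints. The text still does not settle the matter.

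**The primary test may be the overall interaction.** Inflation is then small. However, that test does not isolate the 24-week difference that Section 5.1 names.

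**The size rests on assumed correlations.** This stands. Peak VO2 is the highest 10-second average near the end of a volitional test (Section 7.4), so some visit-specific noise is plausible. Noise moves the figure towards 5%.

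**Unequal variances.** A reader might add that pooling one variance over a 2:1 split also inflates error. With placebo SD 2.3 and anakinra SD 1.7 the figure is about 7.6%; with the SDs reversed it is about 3%. The documents give no arm-specific SDs and no direction, and any pooled t-test has the same property. This is not part of the finding.

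**Conclusion.** The concern holds in conditional form. The covariance structure, the primary contrast and the degrees-of-freedom method are not pre-specified. On the usual reading, with all four visits included, the week-24 standard error is understated if correlation falls with time.

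The conclusion rests on four assumptions: a random intercept only, all visits in the model, the week-24 contrast as the test, and decaying correlation. When all four hold, type I error lies between just above 5% and about 14.5%, depending on the decay and the visit noise. When any one fails, the inflation may shrink or vanish.

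A reader might infer that the trial's p-value is too optimistic or that the test fails its 0.05 level. The documents do not support that as a flat statement, because they give neither the structure nor the correlations. The stated power is not in question.

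**What to change.** In Sections 11.3.1 and 11.3.3, replace the method name with a full specification:

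- a repeated-measures model with group-by-visit means, naming the visits that enter;
- an unstructured visit covariance common to both arms;
- Kenward-Roger degrees of freedom;
- the week-24 treatment contrast as the single primary test;
- if the model does not converge, an analysis of the 24-week change alone.

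Arm-specific variances, if wanted, belong in a sensitivity analysis only.

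The cost is SAP wording and some residual degrees of freedom. With complete data the nominal figure falls from 300 to 100, which moves the critical value from 1.968 to 1.984, under 1%. Power computed with the t distribution is 0.965 at 1.6 with SD 2.0, and 0.918 after 20% loss, so the claims in Section 11.2 stand. A t-test on the 24-week change held 4.6%-5.4% across the simulated patterns.

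The new wording must also say which data set the model uses. Section 11.3.2 carries values forward, while Section 11.3.3 calls for complete cases; the two need to be reconciled whichever model is chosen.

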11.3.2 Handling of Missing Data

Cases with missing data for all follow-up CPX at 6, 12 and 24 weeks will be omitted from the efficacy analysis due to inability to calculate the primary endpoint (change in peak VO_2). Considering that the main variable of interest (peak VO_2) is expected not to improve over time with placebo in patients with systolic HF and exclusion of patient with missing

data would inevitably lead to a survivorship bias, we will use the last observation carried forward (LOCF) method to impute the missing data at 12 and 24 weeks for the primary analysis. We will also perform the Little's Missing Completely At Random (MCAR) test to determine whether the appropriateness of imputing missing values and perform a Multivariate Imputation by Chained Equation (MICE) to validate the finding of peak VO₂ using a different method for data inference.

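### The primary test is not pinned to the week-24 difference in change: 11.3.1 and 11.3.3 list different model terms and missing-data rules differ; separately, baseline peak VO2 goes unused as a covariate

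*Combined protocol and SAP*

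**What the plan says.** Three places agree on the target. Section 5.1: "Placebo-corrected changes in peak VO₂ at CPX after 24 weeks of treatment will be considered the primary endpoint". Section 11.2 sizes the trial on the "difference in interval change in peak VO_2 at 24 weeks between anakinra and placebo". Section 11.3.1 opens its analysis sentence with "The difference in interval changes in peak VO_2 at 24 weeks between the anakinra vs. placebo groups will be compared", and sets the error rate "with statistical significance for the primary endpoint set at the 2-tailed 0.050 level".

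Two sections then describe the model. Section 11.3.1 names a "random-effect analysis of variance for repeated measures to analyze the effects of treatment within each group and the effect of time_x_group allocation". Section 11.3.3, the section on the primary endpoint, says that between-treatment differences in interval change will be compared "using random-effect analysis of variance for repeated measures to analyze the effects of time and group allocation". It gives no interaction and no week.

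The missing-data rules are stated separately. Section 11.3.2: "we will use the last observation carried forward (LOCF) method to impute the missing data at 12 and 24 weeks for the primary analysis". Section 11.3.3: "All analyses will be based on a 'complete case' approach".

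The exercise test is done at baseline and at weeks 6, 12 and 24. Section 7.3 places all baseline testing before study drug is supplied. Section 5.2 makes the week-6 and week-12 changes secondary. No section names a covariate for the primary analysis.

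**The concern.** A repeated-measures analysis of variance produces several tests, and the plan does not say which one carries the primary conclusion. The response could be raw peak VO2 or change from baseline. The visits could be baseline and week 24 only, or all of them. The test could be a group effect, an interaction, or a single contrast. Two analysts, one following 11.3.1 and the other 11.3.3, could run different tests on the same data and differ over which patients and values enter.

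This matters more here because 11.3.3 has the analysis done after lock on groups coded A and B. With 2:1 allocation, group size alone shows which arm is which, so the coding does not replace a fixed test. One test at 0.05 decides the primary conclusion, and 11.1 looks to an exercise-capacity benefit as the rationale for a Phase III trial.

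The covariate is a separate and smaller matter. A pre-treatment value of the outcome is available in every patient who starts treatment and could narrow the interval at no cost in data.

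**Working it through.** **Inputs from the documents.** 68 and 34 patients; 54 and 27 after 20% loss (0.8 × 68 = 54.4; 0.8 × 34 = 27.2). Effect 1.6 mL/kg/min; SD 1.7 to 2.0; two-sided 0.05.

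**Assumptions.** The quoted SD is the SD of change; 11.2 does not say so outright, but step 1 supports it. Step 2 assumes compound symmetry and complete data. Step 3 assumes equal variances at baseline and week 24 and a correlation rho between them of 0.6 to 0.9; the documents give none.

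**Step 1. The plan's own power.** For the single week-24 contrast in change, SE = SD × √(1/n1 + 1/n2), with power from the noncentral t on n1 + n2 − 2 df.
- 68:34, SD 2.0: SE = 2.0 × √(1/68 + 1/34) = 0.420; 1.6/0.420 = 3.81; power 0.965 (0.968 by normal approximation). The table gives 0.97.
- 54:27, SD 2.0: SE = 0.471; 1.6/0.471 = 3.39; power 0.918. The text gives >90%.

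The stated power therefore reproduces, and it is the power of the 1-df week-24 contrast.

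**Step 2. What other terms test if weeks 6, 12 and 24 all enter (68:34, SD of change 2.0).**

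*(a) Interaction on raw values, four visits, 3 df.* Noncentrality = [n1·n2/(n1+n2)] × Σ(δt − mean δ)² / (SD²/2), on 3 and 3(n1+n2−2) = 300 df.

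Take arm differences of 0 at baseline and 1.6/0.8/0 at weeks 6/12/24. The mean is 0.6 and the sum of squares is 0.36 + 1.00 + 0.04 + 0.36 = 1.76. Noncentrality = 22.67 × 1.76/2 = 19.95, giving power 0.97. The test is very likely to be significant although the declared endpoint is null.

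For trajectories that do end at 1.6, power is 0.973 (0.8/1.6/1.6), 0.983 (constant 1.6) and 0.929 (0.4/0.8/1.6). The problem with this test is what it tests, not a general lack of power.

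*(b) Group effect on change scores, averaged over three visits.* The variance of a patient's mean change is (SD²/2) × (1 + 1/3) = 2 × 4/3 = 2.667, so SD 1.633 and SE 0.343.

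| Effect at weeks 6/12/24 | Averaged effect | Power |
|---|---|---|
| 1.6/1.6/1.6 | 1.60 | 0.996 |
| 0.8/1.6/1.6 | 1.33 | 0.97 |
| 0.4/0.8/1.6 | 0.93 | 0.77 |
| 0/0/1.6 | 0.53 | 0.34 |

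All four rows have the same week-24 effect, for which the week-24 contrast has power 0.965. Only in the constant row does the averaged effect equal the week-24 effect.

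**Step 3. Adjusting the week-24 change for baseline (SD of change 2.0).** The variance ratio against the change-score test is (1 + rho)/2: 0.80 at rho 0.6 and 0.95 at rho 0.9, with 1 df lost.

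| | Unadjusted | rho 0.9 | rho 0.6 |
|---|---|---|---|
| 95% CI half-width, 68:34 | 0.833 | 0.812 | 0.746 |
| Power for 1.6, 68:34 | 0.965 | 0.972 | 0.988 |
| Power for 1.6, 54:27 | 0.918 | 0.930 | 0.963 |
| Power for 1.2, 54:27 | 0.710 | 0.732 | 0.803 |

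The unadjusted half-width is 1.984 × 0.420 = 0.833. In sample-size terms, 102/0.95 = 107 and 102/0.80 = 127.5, so adjustment is worth about 5 to 25 patients.

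**Step 4. Missing data.** Under 11.3.2, a patient tested at week 6 but not at week 24 enters with the week-6 value carried forward. Under a complete-case rule for week 24, the same patient is left out. Both rules are written for the primary analysis.

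**The case against.** The strongest reply is that 11.3.3 should be read as a whole sentence. What it sets out to compare is the between-treatment difference in interval change. On raw values with two visits that is exactly the time-by-group term of 11.3.1, and the section heading ties it to an endpoint that 5.1 fixes at 24 weeks. On this view, time and group is shorthand. As a reading of intent, this stands. It does not supply the visits, the response or the contrast, and 11.3.1 does not supply them either.

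A reader might go further and infer that the 11.3.3 group term would miss a true effect of 1.6 in most trials. The documents do not support that. It requires a group effect on raw values with baseline averaged in, which conflicts with the sentence's own object. It also depends on an assumed correlation. Even then it fails within the plan's SD range: with baseline and week 24 in the model, SD 1.7 and rho 0.6, power is 0.60. Under the change-score reading, power is 0.77 or more in three of the four trajectories above.

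It is also fair to say that 11.3.2 only suggests, and does not establish, that all visits enter the model. Step 2 is therefore conditional.

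On missing data, 11.3.2 expressly assigns LOCF to the primary analysis, so the complete-case sentence may be a leftover. It is nevertheless in the current text, in the section on the primary endpoint.

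On the covariate, change from baseline already uses the baseline value and is valid under randomisation. That is right, and the gain for 1.6 at full enrolment is small.

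**Conclusion.** The point holds as a specification gap. The endpoint, error rate, power and sample size agree with one another; the test is not tied to them. If several visits enter, a 3-df interaction can be significant with no week-24 difference (power 0.97 for 1.6/0.8/0), and an averaged change-score effect has power of only 0.77 or 0.34 when benefit builds slowly or comes late. These figures rest on SD of change 2.0, compound symmetry, complete data and illustrative trajectories. They show that the candidate tests differ, not that the trial will lose power.

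The conflict between LOCF and complete case for the same test is on the face of the text and needs no assumption.

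Omitting baseline peak VO2 is missed precision, not an error: 5% to 20% of variance for rho 0.9 to 0.6, with the larger power gains at smaller effects and after dropout. Nothing here calls the stated power or the number of patients into question.

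**What to change.** Put the same sentence in 11.3.1 and 11.3.3: the primary test is the single anakinra-minus-placebo contrast at week 24 in change in peak VO2, adjusted for baseline peak VO2, two-sided at 0.05, reported with its 95% CI. An ANCOVA of the week-24 change on treatment and baseline is enough. If a repeated-measures model is kept, name the response, the visits that enter and the week-24 contrast taken from it.

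State one missing-data rule for this test and refer to it from both 11.3.2 and 11.3.3. Keep the week-6 and week-12 contrasts secondary, as in 5.2, and present within-group changes as descriptive.

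The cost is wording only, before database lock. The baseline test is already collected, and the covariate uses 1 df, which is included in the figures above. Design, visits and sample size do not change.
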